We propose investigating the safety, tolerability and efficacy of adrenocorticotrophic hormone (ACTH, Acthar gel) administered as a pulsed regimen consisting of injections on three consecutive days per month in patients with progressive forms of multiple sclerosis (MS). Safety and tolerability will be assessed by subject-reported adverse events as well as vital signs, physical examination, serologic tests and radiographic measures of bone mineral density. Efficacy will be assessed by changes in walking speed over the course of the study, with the primary endpoint a comparison of the proportion of subjects exhibiting a 20% worsening in the Timed 25-Foot Walk Test (T25FW). We will also explore the effects of ACTH on slowing neurological deterioration via several measures of disability in these patients, including effects on ambulation, cognition, fatigue, vision, and global measures of disability. Finally, we will measure the effect of pulsed ACTH on changes in retinal nerve fiber layer thickness, to assess an important paraclinical measure of neurodegeneration. Because degenerative changes occur at a slow pace, a 3 year study is proposed.

2. Background

MS has both neurodegenerative and inflammatory aspects (1-4)

. In secondary progressive MS (SPMS), the degenerative aspect predominates but inflammation persists, particularly in the early stages, in the form of both occasional acute inflammatory relapses and chronic low-level white matter inflammation. Primary progressive MS (PPMS), by definition, has no clinical relapses but there are MRI abnormalities indicative of inflammation and pathological studies show changes very similar to those seen in SPMS.

While great progress has been made in treating relapsing-remitting MS, **there are no proven safe and effective treatments for progressive forms of MS**. No treatment has been shown to benefit patients with PPMS. The only treatment that has been shown to provide some benefit in SPMS is chemotherapy; the approved immunomodulatory treatments (β -interferons, glatiramer acetate, natalizumab, fingolimod, teriflunomide, and dimethyl fumarate) have not been proven to slow disease progression in this phase of the disease (5). Cyclophosphamide and mitoxantrone have both been shown to slow progression in SPMS, particularly in its early stages, but have obvious disadvantages in terms of toxicity (6-10).

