A key outcome measure of this phase II study is the safety and tolerability of pulsed ACTH compared to placebo. Little background information on adverse effects of pulsed ACTH in MS is available. A preliminary report of a one-year study (17) reported generally no increase in adverse effects in MS subjects receiving pulsed ACTH compared to pulsed MP, and fewer "psychiatric episodes" in the ACTH group. Potential AEs of concern are primarily those related to corticotropin effects, i.e. common steroid-related AEs such as increased risk of infection, weight gain, glucose intolerance, osteoporosis, hypertension, fluid retention, electrolyte derangements, and mood or behavioral changes.

Safety and tolerability of ACTH will be assessed in three ways: via volunteered responses from subjects regarding AEs, by elicited responses regarding specific symptoms, and by laboratory and physical exam measures. The advantage of volunteered (unsolicited) responses is that they allow unexpected AE's to be assessed and tend to highlight more serious or distressing AEs, while elicited responses have the advantage of more sensitive detection of specific AEs of interest (32). The volunteered responses will be obtained by an investigator or study coordinator at each follow-up visit, asking the

subject "Have you had any medical problems since your last visit?" Responses will be recorded on a log and severity will be rated according to the Common Terminology Criteria for Adverse Events (CTCAE) version 4.03. Subjects may also report AE's by phone, and these will be rated and logged in a similar manner. Study personnel will contact subjects monthly (by phone, email, etc.) around the time of their scheduled study drug injections, to remind them of the injections and to check for any new AE. If a phone-reported AE is deemed serious or possibly serious, an unscheduled visit will be arranged to allow the local investigator to assess the AE more fully (see section 7E, Unscheduled Study Visits). Elicited responses will be assessed through a questionnaire that will explore insomnia, irritability, dyspepsia, injection pain, edema, dysgeusia, fatigue, vision, skin changes, and changes in menstruation.

Physical exam and laboratory measures will include objective measurements of weight, blood pressure, skin changes, edema, myopathy, cataracts, glucose, electrolyte abnormalities, bone mineral density (DEXA) and hepatic toxicity.

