Each subject will have OCT performed on each eye at baseline and then annually for 3 years (total of 4 OCT per subject). OCT will be performed on the Spectralis OCT system (Heidelberg Engineering, Germany) using the glaucoma protocol set. If the study center's available Spectralis OCT system has the neurology-oriented "N-site" software, then the RNFL scan (see below) will be obtained twice, once using the glaucoma protocol set and once using the axonal (N-site) protocol set. Pupillary dilation will not be routinely performed, as it is usually unnecessary for OCT (49). If dilation is deemed necessary to achieve adequate OCT quality (e.g., due to cataract), the subject may be excluded from the OCT portion of the study. Alternatively, dilation may be performed (with typical mydriatic eye drops) if the dilation and OCT are done after the other functional study assessments (e.g. EDSS, MSFC, LCVA, BRB-N) during the study visit, or if dilation/OCT are done on a separate visit day within a +/- 2 week window of other efficacy measures. In other words, pupillary dilation for OCT purposes will not be allowed to interfere with the other efficacy assessments that require vision for their performance.

Up to three different scans will be performed on each eye at each visit, to assess RNFL thickness, macular volume, and individual retinal layer thickness (ganglion cell layer, inner nuclear layer, etc). The RNFL scan will be obtained twice (once using the glaucoma protocol and once using the axonal protocol) if the axonal protocol is available. The axonal protocol (N-site) is optimized for detecting abnormalities in MS, and is thus the preferred method. However, all of the study sites are not expected to have access to the axonal protocol, while all will have the glaucoma protocol available. Therefore, we will obtain all scans on the glaucoma protocol (to ensure consistency of data), and acquire the axonal protocol RNFL scan as well when it is an option. The scans to be obtained are:

- i. **RNFL scan (circle scan)** – Standard settings for peripapillary RNFL with the Spectralis glaucoma protocol will be used: 12 degree (3.45 mm) circular scan manually centered on the optic disc, ART = 100, circle = 12°, 768 A-scans.
- ii. **Macular volume scan (posterior pole scan)** – The posterior pole scan from the glaucoma protocol set will be used, again using the standard settings: 30x25, 61 sections, 760 A-scans per section, distance between B-scans = 120 μ m, ART = 9.

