Multiple linear regression models will be used to test for between group differences in LCVA scores adjusted for other covariates. Binocular LCVA scores will be used to test for a treatment effect on vision changes; monocular LCVA scores will be used for correlation with OCT measures (from the matching eye). Generalized estimating equation (GEE) models will be used to test for between group differences in change over time in vision loss rates adjusted for other covariates. In addition correlation of LCVA with OCT measures (RNFL and macular volume) will be evaluated using Pearson correlation analysis (Spearman correlation will be used if measures have skewed distributions).

Between group differences in mean OCT macular volume scan measures will be tested using multiple linear regression models adjusted for covariates. mixed model analyses of repeated measures will be used to test for between group differences in change over time in OCT macular volume measures.

7. Study Procedures

A. Schedule of study procedures:

1. Symptoms questionnaire for subjective adverse events at baseline, 3, 6 and 12 months and then annually.
2. Comprehensive metabolic panel (CMP) and hemoglobin A1C (HbgA1C) at screening, 6 and 12 months, and then annually.
3. EDSS and DEXA scan (both hips/femurs and lumbar spine) at screening and then annually.
4. OCT at baseline and then annually.
5. MSFC, T25FW, 6MWT, LCVA, MSWS-12, AI, FSS and BRB-N at baseline and then annually.
6. Practice sessions (at screening visit:
 - a. BRB-N - 1 practice session

- b. PASAT - 2 practice sessions (in addition to the one administered during BRB-N)
- c. 9HP - 3 practice sessions

Table 1. Study Schedule

	V1 Screen 0 to -4 wks	V2 Baseline M0	V3 *** M3	V4 M6	V5 M12	V6 M18	V7 M24	V8 M30	V9 M36
Informed Consent	X								
Inclusion/Exclusion	X								
Injection Training		X							
Blood Pressure		X	X	X	X	X	X	X	X
Weight		X	X	X	X	X	X	X	X
Safety Lab Tests^a	X			X	X		X		X
Skin & Edema Assessment		X	X	X	X	X	X	X	X
OCT		X			X		X		X
LCVA		X			X		X		X
EDSS	X				X		X		X
Timed 25-Ft Walk		X			X		X		X
9-Hole Peg Test	XXX	X			X		X		X
PASAT (apart from BRB-N)	XX								
6 Minute Walk Test		X			X		X		X
MS Walking Scale - 12		X			X		X		X
Fatigue Severity Scale (FSS)		X			X		X		X
Hauser Ambulation Index		X			X		X		X
Brief Repeatable Battery	X	X			X		X		X
DEXA Scan^b	X ^c				X		X		X
Randomization		X							
Symptom Questionnaire		X	X	X	X	X	X	X	X
Concomitant Medications		X	X	X	X	X	X	X	X

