Unsolicited Adverse Events			X	X	X	X	X	X	X
Dispense Study Drug		X	X	X	X	X	X	X	
Return Drug Vials and Logs			X	X	X	X	X	X	X

^a Safety lab tests: comprehensive metabolic panel and hemoglobin A1C.

^b Bilateral hips and lumbar spine

^c DEXA scan may be omitted at the Screening Visit if subject provides results of DEXA scan done within the 3 months prior to the Screening Visit

*** The month 3 visit is primarily a safety visit to assess AEs and to assess any difficulties subjects may be having with study drug injections. No laboratory tests are done, and no physical exam other than the skin and edema assessment (which would be unlikely to yield abnormal findings at 3 months, since chronic steroid side effects would likely take longer to occur in the 3 day per month pulsed dosing). For patients traveling a long distance to the study, this visit might be much more conveniently done by phone.

While the preference is for the month 3 visit to be done on-site, it can (optionally) be done as a phone visit, e.g. for subjects who 1) are inconvenienced by coming in person for this visit, and 2) have prior experience with taking subcutaneous injections. If this option is chosen, then 1) 6 months' worth of study drug (rather than 3) must be given out at the baseline visit, 2) no study drug dispensing or drug return will occur at the month 3 visit, and 3) no skin and edema assessment will be done at the month 3 visit.

B. Treatment Administration:

ACTH (Acthar gel) and placebo will be provided by the funding sponsor and distributed to individual sites. The study medication will be self-administered at a dose of 80 units subcutaneously for 3 consecutive days every month for the duration of the study. The dose will be reduced to 40 units if the full dose cannot be tolerated. Specific training in the injection procedure will be done prior to the initial injection.

C. Study Staff

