Each study site will have a local principal investigator (Fargo, [name]; Minneapolis, [name]; Milwaukee, [name]; other sites may be added in the future) who will oversee study operation at that site and be responsible for the acquisition and handling of study data according to the procedures outlined in this protocol. Each site will utilize a study neurologist or neurology nurse practitioner certified in EDSS administration, who will perform the EDSS, review safety and tolerability data and report AEs and SAEs. There will not be a separate "treating" and "examining" neurologist at each site. A backup study neurologist may be designated, in case the primary study neurologist is unavailable for a scheduled visit. Other study staff such as research coordinators or nurses may be assigned to assist in recruitment, scheduling, and study procedures. Study coordinators/nurses may administer all study assessments except the EDSS and the physical examination (e.g., MSFC, BRB-N, 6MWT, MSWS-12, AI, LCVA, and subject-reported AE assessments), as long as they have been specifically and adequately trained on administering these assessments. Alternatively, the site study neurologist (or backup) may administer these assessments as well. OCT and DEXA scans will be performed by operators trained in administering those tests. A study monitor will be designated from the primary study site (University of Minnesota, Minneapolis) and will oversee data collection and management, as well as visit all study sites to review compliance with study procedures.

D. Relapses

Patients with certain forms of progressive MS (SPMS, PRMS) may experience acute disease relapses in addition to gradual neurologic decline. MS relapses entail new or worsened

neurologic symptoms that typically evolve over days, last for weeks, and gradually improve. They commonly manifest as focal deficits in sensory and/or motor function, visual disturbance, brainstem/cerebellar symptoms (such as vertigo, diplopia or ataxia), bladder or bowel symptoms, gait impairment, or fatigue. Acute cognitive or behavioral symptoms are less common, but may occur. Relapse symptoms may eventually resolve completely, partially, or not at all.

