Subjects will be asked to contact their study site if they develop new symptoms that are concerning to them. The local study coordinator will record the reported symptoms on the Unsolicited AE Form, which will be reviewed by the local investigator. An unscheduled study visit will occur if the local investigator deems these AEs as potentially serious, possibly related to study medication, and/or requiring in-person assessment. If the reported symptoms are interpreted as mild and/or unrelated to study medication, the subject may be referred to their primary physician or advised to report back by phone with updates about symptom

evolution/resolution. Unscheduled visits will not be routinely performed for suspected MS relapse (see section 7D, Relapses), although they may occur in this situation if the reported symptoms are interpreted as a possible treatment-related AE. Assessments/procedures performed at an unscheduled visit will include all of the assessments done at Visit 3 (see Table 1) with the exception of study drug distribution; any further assessments and/or procedures (e.g. physical examination, other tests, referrals) will be done at the discretion of the local investigator.

F. Early Termination and Intent to Treat

Once subjects are randomized, regardless of if or the length of time they have been on blinded treatment, they will be included in the efficacy (intent to treat) analysis if efficacy data are available (that is, if they have completed at least one annual follow-up visit). Subjects who withdraw (e.g., due to side effects) prior to completing the Month 12 visit will be asked to return the study drug to the site, and to participate in annual phone calls (Months 12 and 24), and to return to the site for the final visit at Month 36. Subjects who withdraw after completing the Month 12 visit will be asked to return the study drug to the site, and to complete the remaining annual study visits (i.e., Month 24 and Month 36) even though they are not receiving drug. Subjects are of course allowed to decline further participation, in which case they would be considered lost-to-follow-up.

G. Data Safety Monitoring

A DSMB will be formed and will consist of one MS specialist, one neurologist familiar with the evaluation and treatment of MS but not otherwise associated with the study, and the study biostatistician. A DSMB chairperson will be chosen from one of the two neurologists on the DMSB.

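### Section 5.B promises objective measurement of myopathy and cataracts, but the schedule, adverse-event definitions and named analyses assess neither, and OCT data may be lost after randomisation for a possibly drug-related reason

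*Combined protocol and SAP*

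**What the plan says.** Section 5.B sets out three routes to safety data: volunteered reports, elicited symptoms, and examination and laboratory findings. For the third it promises "objective measurements of weight, blood pressure, skin changes, edema, myopathy, cataracts, glucose, electrolyte abnormalities, bone mineral density (DEXA) and hepatic toxicity". The Abstract likewise counts "vital signs, physical examination, serologic tests and radiographic measures of bone mineral density" among the safety measures. Section 6.B describes safety and tolerability over three years as the study's main objective.

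The operational sections are narrower:

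- In Table 1, apart from blood pressure, weight and the EDSS, the only examination row is "Skin & Edema Assessment". The laboratory footnote reads "Safety lab tests: comprehensive metabolic panel and hemoglobin A1C". The note on the month 3 visit says there is "no physical exam other than the skin and edema assessment".
- Section 7.C states: "Study coordinators/nurses may administer all study assessments except the EDSS and the physical examination". It gives the physical examination no visit and no content.
- Section 7.E, on unscheduled visits, says that "any further assessments and/or procedures (e.g. physical examination, other tests, referrals) will be done at the discretion of the local investigator".
- Section 5.G, on scans that need dilation, reads "e.g., due to cataract), the subject may be excluded from the OCT portion of the study". It then offers dilation as an alternative, either after the other functional assessments or on a separate day within two weeks of them.

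**The concern.** A measure that is promised but never scheduled tends not to be collected, or to be collected differently at each site. Without a baseline, a finding at month 24 cannot be called new. Without systematic follow-up, a report of few or no cases says little about whether the drug causes them. That matters more than usual here because safety is the stated main objective.

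Two efficacy measures are also touched. Drug-related leg weakness would slow walking, and the primary endpoint in Section 5.A counts any 20% slowing whatever its cause. Cataract can degrade OCT scans, and change in temporal-quadrant retinal nerve fibre layer (RNFL) thickness is a secondary endpoint. If lens opacity were more frequent on active drug, excluding those subjects after randomisation would remove data unequally by arm.

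**Working it through.** **Step 1. Promised items against the plan.** The ten items in Section 5.B, traced through Section 7.A and Table 1:

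| Item in 5.B | Where it is measured |
|---|---|
| Weight | Own row, baseline to month 36 |
| Blood pressure | Own row, baseline to month 36 |
| Skin changes, edema | One combined row, baseline to month 36 |
| Glucose, electrolytes, hepatic toxicity | Safety laboratory row (metabolic panel, HbA1c) |
| Bone mineral density | DEXA row, screening and annually |
| Myopathy | None |
| Cataracts | None |

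Count: 1 + 1 + 2 + 3 + 1 = 8 scheduled, and 10 − 8 = 2 not scheduled.

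**Step 2. Other places that might supply the missing two.**

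- Protocol-defined adverse events (5.B): seven items, covering weight, blood pressure, HbA1c, potassium and three DEXA criteria. Neither condition is listed.
- Named examination and laboratory analyses (6.E): weight, blood pressure, HbA1c, electrolytes and bone density. Neither condition is listed. Absence from these two lists alone would prove little, because skin changes, edema and hepatic toxicity are absent too. What singles out myopathy and cataracts is that they are also missing from the schedule.
- Elicited questionnaire (5.B): it asks about fatigue and vision. It does not ask about muscle weakness, and it is self-report.
- EDSS (5.F): examination-based, but it rates MS disability, and no myopathy item is described.
- OCT (5.G): operators judge scan quality only, with no clinical interpretation. Cataract is mentioned only as a cause of poor quality.
- Physical examination (7.C, 7.E): mentioned, but without a scheduled visit or content.

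**Step 3. The OCT exclusion.** The permission in 5.G carries no time limit, so it applies equally at baseline and at months 12, 24 and 36. An exclusion at baseline cannot depend on treatment; one at a later visit can.

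**Step 4. What weakness could do to the primary comparison (illustration only).** The plan's own figure reproduces. With P1 = 0.6, P2 = 0.3, two-sided α = 0.05 and 80% power:

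n = [1.96 × √(2 × 0.45 × 0.55) + 0.842 × √(0.6 × 0.4 + 0.3 × 0.7)]² / 0.3² = 42 per arm.

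The documents give no rate of myopathy. As an assumption, let a share m of ACTH subjects who would otherwise not worsen cross the 20% threshold because of weakness. The ACTH rate becomes 0.30 + 0.70m. Power at 42 per arm against 0.60 is then:

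| m (assumed) | ACTH rate | Power |
|---|---|---|
| 0 | 0.300 | 0.80 |
| 2% | 0.314 | 0.76 |
| 5% | 0.335 | 0.69 |
| 10% | 0.370 | 0.56 |

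The effect runs one way: it dilutes an apparent benefit and cannot create one.

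**The case against.** The strongest reply has five parts.

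1. *The conditions can still be reported.* Volunteered events are collected at every follow-up visit, with a check at monthly contacts. They are graded by CTCAE, and specific event rates are compared by Fisher's exact test. A reader might infer from the schedule gap that the trial cannot report myopathy or cataract at all; the documents do not support that. What remains is that 5.B itself credits elicited questions with greater sensitivity and presents objective measurement as a separate route.
2. *An examination is foreseen.* Sections 7.C and 7.E mention one, the month 3 restriction is specific to that visit, and the EDSS examiner reviews safety data. This stands in part, but nothing says when the physical examination is done, what it covers or where it is recorded.
3. *The primary comparison is sound.* A reader might infer that unmeasured myopathy invalidates the walking endpoint. It does not: the trial is randomised, double-blind and placebo-controlled, so the arms are validly compared on the net effect. The plan never undertakes to separate causes of slowing. This stands in full.
4. *OCT loss is optional and need not be unexplained.* Section 5.G says a subject may be excluded, offers dilation instead, and does not say that the reason goes unrecorded. Vision is also asked about, and acuity is tested annually at three contrast levels. This stands; the residue is a permission with no time limit.
5. *Neither condition is a headline concern.* The paragraph of 5.B that lists adverse effects of concern names neither. This supports a moderate priority and makes deletion a legitimate remedy.

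**Conclusion.** The inconsistency is established from the text: two of ten promised objective safety measures have no assessment at any of the nine scheduled visits, no event definition and no named analysis. They can surface only as volunteered events, indirectly through the vision and fatigue questions, or in a physical examination of unstated timing and content. The consequence is under-ascertainment without a baseline, so a low count would not show absence.

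For efficacy, the loss is explanatory. If the trial shows no benefit, there will be no systematic strength record with which to explore whether toxicity offset part of one. The power figures above rest wholly on assumed values of m. Nor can the number of missed cases be estimated, because the documents give neither an incidence for either condition nor a probability of detection.

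The OCT point is a separate, smaller risk. It assumes that sites use the exclusion after randomisation and that the need for dilation differs by arm; the documents permit the first and are silent on the second.

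This should be corrected, but it does not threaten the primary comparison or the sample size.

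**What to change.** Reconcile Section 5.B with Section 7.A and Table 1, using visits that already exist.

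1. At each EDSS examination (screening, months 12, 24 and 36), record proximal limb strength as a separate safety item. Add one sentence to Section 6.E comparing change from screening between arms. State that the item is not specific in MS; it gains meaning from the subject's own baseline and the blinded comparison.
2. At each OCT session (baseline, months 12, 24 and 36), record the reason for poor quality or dilation as a scan-quality field. The site investigator then reviews it for adverse-event logging. This keeps operators within the quality-only role in Section 5.G. The field catches only opacity that affects the scan, so 5.B should describe it as such and not as a lens examination.
3. Limit the exclusion in Section 5.G to baseline. After randomisation, use the dilation route that the section already permits.
4. If the strength and lens items will not be recorded, remove myopathy and cataracts from the list in 5.B, so that no safety statement rests on them.

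The cost is two case report form fields, a few sentences of text, a few minutes at each annual visit, and occasional dilation.
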